16.2.2.14 Section 5.1.1.2: Switching from heparin/fondaparinux to rivaroxaban

This section was modified based on Amendment Change 2.

Old text: If the child received heparin treatment before ~~randomization, randomization~~ should be planned 4 hours after stopping the infusion of UFH, 6 - 12 hours after the last injection of LMWH with a twice-daily regimen, or 12 - 24 hours after the last injection of fondaparinux or LMWH with a once-daily regimen. Heparin/fondaparinux treatment cannot be continued after the start of rivaroxaban treatment in these children.

New text: If the child received heparin treatment before study treatment with rivaroxaban, rivaroxaban administration should be planned 4 hours after stopping the infusion of UFH, 6 - 12 hours after the last injection of LMWH with a twice-daily regimen, or 12 - 24 hours after the last injection of fondaparinux or LMWH with a once-daily regimen. Heparin/fondaparinux treatment cannot be continued after the start of rivaroxaban treatment in these children

16.2.2.15 New Section 5.1.1.3: Switching from rivaroxaban to heparin/fondaparinux

This section was modified based on Amendment Change 5.

New text: **5.1.1.3: Switching from rivaroxaban to heparin/fondaparinux**
Children who switch from rivaroxaban to heparin /fondaparinux can switch at the time of the next scheduled dose.

16.2.2.16 New Section 5.1.1.4: Switching from rivaroxaban to VKA

This section was modified based on Amendment Change 5.

New text: **5.1.1.4: Switching from rivaroxaban to VKA**
Children who switch from rivaroxaban to VKA need to continue rivaroxaban for 48 hours after the first dose of VKA. After 2 days of co-administration, an INR should be obtained prior to the next scheduled dose of rivaroxaban. Co-administration of rivaroxaban and VKA is advised to continue until the INR is ≥ 2.0 .

16.2.2.17 Section 5.1.2: Comparator group

This section was modified based on Amendment Change 2.

Old text: ~~Children randomized to the comparator group will continue with the anticoagulant treatment that was planned prior to study randomization. Thus, children who received heparins/ fondaparinux before randomization, continue with it after randomization. Children, who received VKA before randomization, continue with VKA after randomization. VKA dosages will be adjusted to maintain the INR within the therapeutic range (target 2.5, range 2.0 – 3.0). VKA therapy will be administered according to local guidelines. If a VKA dose was missed, it can only be taken the same day. Double dosing on a single day is not allowed.~~

New text: This single-arm study does not include comparator treatment.

16.2.2.18 Section 5.2: Subject identification

This section was modified based on Amendment Change 2.

Old text: SID numbers will have to be used in sequence and no number should be skipped or substituted.

~~At Visit 2, Day 1, children will be assigned a unique randomization number by IxRS that will allow subsequent identification of treatment allocation.~~

New text: SID numbers will have to be used in sequence and no number should be skipped or substituted.

16.2.2.19 Section 5.4.1: Rivaroxaban

This section was modified based on Amendment Change 1.

Old text: Rivaroxaban will be provided by Bayer as a 0.1% suspension. Rivaroxaban will be dosed according to body weight groups (see Table 5-1). Since children with a glomerular filtration rate below 30 mL/min/1.73 m² are excluded from the study, a dose adaptation is not indicated.

New text: Rivaroxaban will be provided by Bayer as a 0.1% (**1mg/ml**) suspension. Rivaroxaban will be dosed according to body weight groups (see Table 5-1). Since children with a glomerular filtration rate below 30 mL/min/1.73 m² are excluded from the study, a dose adaptation is not indicated.

16.2.2.20 Section 5.4.2: Comparator

This section was modified based on Amendment Change 2.

Old text: ~~Comparator will be used according to approved formulations~~

New text: This single-arm study does not include comparator treatment.

16.2.2.21 Section 5.5: Packaging, labeling, and storage

This section was modified based on Amendment Change 2.

Old text: ~~Comparator will be supplied from local commercial resources and provided by sites. If required by local regulations, Bayer will purchase the comparator from local sources, and label and distribute to investigative centers.~~

[...]

Comparator provided by sites will be documented in the hospital/pharmacy records.

16.2.2.22 Section 5.6: Treatment assignment

This section was modified based on Amendment Change 2.

Old text: ~~After randomization, the randomization number of the child will be recorded on the corresponding electronic case report form (eCRF). Subject identification number will have to be recorded on the label of the study medication.~~

~~In case LMWH, fondaparinux and/or VKA is provided by sites, the compound's name, dose, quantity and batch number or a copy of the prescription must be included in the child's files.~~

New text: Not applicable.

16.2.2.23 Section 5.7: Dosage and administration

This section was modified based on Amendment Change 2.

Old text: ~~Comparator treatment consists of locally used anticoagulants for VTE treatment, specified in Table 5-2.~~

Table 5-2: Overview of comparator treatment

Generic name	Dosage
Warfarin	INR 2.0-3.0
Acenocoumarol	INR 2.0-3.0
Phenprocoumon	INR 2.0-3.0
Enoxaparin	1 mg/kg b.i.d.
Fondaparinux	0.1 mg/kg o.d.
Tinzaparin	2-12 mo — 250 u/kg o.d. 1-5 yrs — 240 u/kg o.d. 5-10 yrs — 200 u/kg o.d.
Dalteparin	129 ± 43 u/kg/dose o.d.

b.i.d.: twice daily; o.d.: once daily; u:units

Source: (10)

~~The comparator list above is not all-inclusive.~~

New text: Rivaroxaban will be dosed according to body weight as oral 0.1% suspension.

16.2.2.24 Section 5.8: Treatment compliance

This section was modified based on Amendment Change 2.

Old text:

~~5.8.2 Vitamin K antagonists~~

~~Compliance with VKA treatment will only be ensured by the use of INR, with a minimum of 1 INR per 2 weeks. The date of first and last intake with specifications of the brand and all INR values and the actual measurement dates will be documented. This information will be obtained directly from the child's file or transmitted by the INR monitoring physician or laboratory.~~

~~5.8.3 Low molecular weight heparin/fondaparinux~~

~~Instruction will be given to return all unused syringes at Visit 3, Visit 4 and, if applicable, at the premature discontinuation visit. Compliance will be evaluated by counting remaining syringes. All non-dispensed syringes should be kept securely in the original containers in a designated locked container until retrieved or dispensed.~~

16.2.2.25 Section 6.1: Study visits

This section was modified based on Amendment Change 2.

Old text: Visit 1 is a screening visit and will be a hospital visit. This visit is to identify potential eligibility of children who are treated with anticoagulants for confirmed symptomatic or asymptomatic venous thrombosis. This visit will take place 60 to 10 days before ~~the last month of intended anticoagulation treatment.~~

Visit 2 is the ~~randomization visit~~ and will be a hospital visit. Eligible children will ~~be randomized to 30 days of anticoagulation with study medication (day 1).~~

Visit 3 and Visit 4 are the treatment and end of treatment visits, respectively. These visits will be hospital visits which will take place at Day 15 ± 5 days, and Day 30 ± 3 days, respectively. At visit 2, 3 and 4, PK/PD blood ~~sampling will be done in the rivaroxaban group only.~~ At Visit 4, the study medication will be stopped. After cessation of study treatment, it is at the investigator's discretion to continue with anticoagulation, as needed. Repeat imaging will be obtained if applicable.

New text: Visit 1 is a screening visit and will be a hospital visit. This visit is to identify potential eligibility of children who are treated with anticoagulants for confirmed symptomatic or asymptomatic venous thrombosis. This visit will take place 60 to 10 days before Visit 2.

Visit 2 is the first study drug administration day and will be a hospital visit. Eligible children will receive rivaroxaban for 30 days.

Visit 3 and Visit 4 are the treatment and end of treatment visits, respectively. These visits will be hospital visits which will take place at Day 15 ± 5 days, and Day 30 ± 3 days, respectively. At visit 2, 3 and 4, PK/PD blood samples will be drawn. At Visit 4, the study medication will be stopped. After cessation of study treatment, it is at the investigator's discretion to continue with anticoagulation, as needed. Repeat imaging will be obtained if applicable.

16.2.2.26 Section 6.2: Visit 1 - Screening visit at 60 to 10 days before Visit 2

This section was modified based on Amendment Change 2.

Old text: Adverse events will not be collected between visit 1 and visit 2. Since hemoglobin, platelet counts, creatinine and liver function tests are performed as part of routine clinical practice in children treated with anticoagulants, recent results will be available and, therefore, a blood sample is not required as part of the study screening assessments. Availability of results for hemoglobin, platelets, creatinine, ALT, and bilirubin within 10 days prior to ~~randomization~~ is an inclusion criterion for this study (see section 4.2).

New text: Adverse events will not be collected between visit 1 and visit 2. Since hemoglobin, platelet counts, creatinine and liver function tests are performed as part of routine clinical practice in children treated with anticoagulants, recent results will be available and, therefore, a blood sample is not required as part of the study screening assessments. Availability of results for hemoglobin, platelets, creatinine, ALT, and bilirubin within 10 days prior to Visit 2 is an inclusion criterion for this study (see section 4.2)

16.2.2.27 Section 6.3. Visit 2 - Treatment visit at Day 1

This section was modified based on Amendment Change 1 and 2.

Old text: **6.3. Visit 2 - ~~Randomization~~ visit at Day 1**

If the CIAC confirmed the qualifying venous thrombotic event, then re-confirm eligibility. If results for hemoglobin, platelets, creatinine, ALT, bilirubin were not available within 10 days prior to ~~randomization~~, obtain blood sample. If the child still meets the inclusion criteria and does not meet any of the exclusion criteria, the child can be ~~randomized~~.

- If a child is on VKA therapy and has a supra-therapeutic INR (> 3.0), ~~randomization into the study should be delayed. In case of an INR below 3.0, randomization can be done. If randomized to VKA, treatment with VKA should continue. If randomized to rivaroxaban, VKA should be stopped and the timing of the administration of the first rivaroxaban dose will depend on the INR (see also section 5.1.1.1).~~

If the INR is below 2.5, the first rivaroxaban dose should be taken ~~on the day of randomization~~.

[...]

- Administer ~~the assigned study drug~~
- ~~In children allocated to rivaroxaban,~~
- ~~administer the first rivaroxaban dose and document~~ the volume and type of fluid used to predilute the rivaroxaban oral suspension, as well as the volume and type of fluid taken after the study drug administration.
- ~~document~~ the exact time of drug intake and the time and type of meal (e.g. breast feeding, baby bottle, porridge, breakfast, lunch, snack, dinner) the child took 2 hours before, during and after study drug administration.
- ~~at~~ 0.5-1.5 hr after drug intake, collect only a PK blood sample
- ~~at~~ 2.5-4 hr after drug intake, collect a PK blood sample followed by the PD blood sample.

[...]

- ~~In children allocated to rivaroxaban, instruct~~ to 1) document in the study booklet the exact time of the last dose taken on the day prior to Visit 3, 2) the exact time and type of meal the child took 2 hours before, during and after study drug administration, 3) the volume and type of fluid used to predilute the rivaroxaban oral suspension and 4) the volume and type of fluid taken after the study drug administration.

[...]

New text: **6.3. Visit 2 - Treatment visit at Day 1**

If the CIAC confirmed the qualifying venous thrombotic event, then re-confirm eligibility. If results for hemoglobin, platelets, creatinine, ALT, bilirubin were not available within 10 days prior to Visit 2, obtain blood sample. If the child still meets the inclusion criteria and does not meet any of the exclusion criteria, the child can receive rivaroxaban.

- If a child is on VKA therapy and has a supra-therapeutic INR (> 3.0), the first administration of rivaroxaban should be delayed VKA therapy should be stopped and the timing of the administration of the first rivaroxaban dose will depend on the INR (see also section 5.1.1.1).

If the INR is below 2.5, the first rivaroxaban dose should be taken at Visit 2.

[...]

- Administer first dose of rivaroxaban oral suspension
- Document the volume and type of fluid used to predilute the rivaroxaban oral suspension, as well as the volume and type of fluid taken after the study drug administration.
- Document the exact time of drug intake and the time and type of meal (e.g. breast feeding, baby bottle, porridge, breakfast, lunch, snack, dinner) the child took 2 hours before, during and after study drug administration.
- At 0.5-1.5 hr after drug intake, collect only a PK blood sample
- At 2.5-4 hr after drug intake, collect a PK blood sample followed by the PD blood sample.

[...]

- Instruct to 1) document in the study booklet the exact time of the last dose taken on the day prior to Visit 3, 2) the exact time and type of meal the child took 2 hours before, during and after study drug administration, 3) the volume and type of fluid used to predilute the rivaroxaban oral suspension and 4) the volume and type of fluid taken after the study drug administration.

[...]

16.2.2.28 Section 6.4: Visit 3 - Treatment visit at Day 15 (+/- 5 days)

This section was modified based on Amendment Change 1 and 2.

Old text: [...]

- ~~In children randomized to rivaroxaban~~
- ~~administer~~ the next rivaroxaban dose and document the volume and type of fluid used to predilute the rivaroxaban oral suspension, as well as the volume and type of fluid taken after the study drug administration.
- ~~document~~ the exact time of drug intake and type of meal the child took 2 hours before, during and after drug administration
- ~~complete~~ the Taste-and-Texture Questionnaire for children older than 4 years
- ~~at~~ 2 – 8 hr after drug intake, collect a post-dose PK blood sample followed by the PD blood sample
- ~~document~~ the exact time of blood sampling for PK/PD.

[...]

- ~~In children allocated to rivaroxaban, inform~~ that on the day before visit 4

[...]

New text: [...]

- Administer the next rivaroxaban dose and document the volume and type of fluid used to predilute the rivaroxaban oral suspension, as well as the volume and type of fluid taken after the study drug administration.
- Document the exact time of drug intake and type of meal the child took 2 hours before, during and after drug administration
- Complete the Taste-and-Texture Questionnaire for children older than 4 years
- At 2 – 8 hr after drug intake, collect a post-dose PK blood sample followed by the PD blood sample
- Document the exact time of blood sampling for PK/PD.

[...]

- Inform that on the day before visit 4

[...]

16.2.2.29 Section 6.5: Visit 4 - End of study treatment visit at Day 30 (+/- 3 days)

This section was modified based on Amendment Change 2.

Old text: [...]

- ~~In children randomized to rivaroxaban~~

[...]

16.2.2.30 Section 6.9: Recommendations before and after invasive procedures and surgical intervention

This section was modified based on Amendment Change 2.

Old text: ~~For the comparator please follow the respective product label.~~

16.2.2.31 Section 6.10: Management of bleeding in children

This section was modified based on Amendment Change 2.

Old text:

- ~~Delay the next LMWH, fondaparinux, VKA or rivaroxaban administration or discontinue treatment, if indicated~~
- ~~If the child is treated with VKA, consider vitamin K administration~~
- ~~If the child is treated with LMWH, consider protamine sulfate administration~~
- [...]
- ~~If the child is treated with rivaroxaban, obtain the PK/PD sample.~~

New text:

- [...]
- Obtain the PK/PD sample.

16.2.2.32 Section 6.12: PK/PD assessments

This section was modified based on Amendment Change 2.

Old text: Blood samples will be taken for PK and PD measurements ~~from children randomized to rivaroxaban~~. The number and volume of PK/PD blood samples represents the minimum amount of blood needed for adequate analysis (sparse sampling approach). The following blood samples will be taken:

New text: Blood samples will be taken for PK and PD measurements. The number and volume of PK/PD blood samples represents the minimum amount of blood needed for adequate analysis (sparse sampling approach). The following blood samples will be taken:

16.2.2.33 Section 6.13: Study booklet

This section was modified based on Amendment Change 2.

Old text: Parents/children will receive a booklet with the following information ~~for both treatment groups:~~

[...]

For the rivaroxaban treatment group

[...]

For the comparator group

- ~~How to use comparator~~
- ~~The planned dates of blood collections for the next INR control, if VKA is used~~
- ~~Instruction to insert the INR values (if available).~~

New text: Parents/children will receive a booklet with the following information:

[...]

16.2.2.34 Section 7.2: Analysis sets

This section was modified based on Amendment Change 2.

Old text: Full analysis set (FAS): This analysis set will include all ~~randomized~~ children.

Safety analysis set (SAS): This analysis set will include all ~~randomized~~ children who received at least one dose of study medication.

Per protocol set (PPS): This population includes all ~~randomized~~ children who completed the 30-day treatment period. The PPS may also exclude major protocol deviations. Further details will be specified in the Statistical Analysis Plan.

New text: Full analysis set (FAS): This analysis set will include all enrolled children.

Safety analysis set (SAS): This analysis set will include all enrolled children who received at least one dose of study medication.

Per protocol set (PPS): This population includes all enrolled children who completed the 30-day treatment period. The PPS may also exclude major protocol deviations. Further details will be specified in the Statistical Analysis Plan.

16.2.2.35 Section 7.3: Demographic and other baseline characteristics

This section was modified based on Amendment Change 2.

Old text: Summary statistics (arithmetic mean, standard deviation, median, minimum and maximum for quantitative variables) will be presented by ~~treatment~~. Frequency tables for qualitative data will be provided. Medical history findings will be summarized using Medical Dictionary for Regulatory Activities (MedDRA) terms.

New text: Summary statistics (arithmetic mean, standard deviation, median, minimum and maximum for quantitative variables) will be presented by age group. Frequency tables for qualitative data will be provided. Medical history findings will be summarized using Medical Dictionary for Regulatory Activities (MedDRA) terms.

16.2.2.36 Section 7.4: Safety analysis

This section was modified based on Amendment Change 2.

Old text: Individual listings of major and clinically relevant non-major bleeding will be provided. The incidence of bleeding will be summarized ~~by treatment~~. If a sufficient number of bleeding events is observed, factors which potentially influence the occurrence of bleeding will be assessed by appropriate statistical procedures.

Quantitative data will be described by the summary statistics and will be presented ~~by treatment for~~ the original data as well as for the difference to baseline. Frequency tables will be provided for qualitative data.

New text: Individual listings of major and clinically relevant non-major bleeding will be provided. The incidence of bleeding will be summarized descriptively. If a sufficient number of bleeding events is observed, factors which potentially influence the occurrence of bleeding will be assessed by appropriate statistical procedures.

Quantitative data will be described by the summary statistics and will be presented descriptively for the original data as well as for the difference to baseline. Frequency tables will be provided for qualitative data.

16.2.2.37 Section 7.5: Efficacy analysis

This section was modified based on Amendment Change 2.

Old text: All efficacy analyses will be performed on the FAS population. The occurrence of recurrent venous thromboembolism and asymptomatic deterioration in thrombotic burden will be summarized by ~~treatment~~.

New text: All efficacy analyses will be performed on the FAS population. The occurrence of recurrent venous thromboembolism and asymptomatic deterioration in thrombotic burden will be summarized by age group.

16.2.2.38 Section 7.8: Determination of sample size

This section was modified based on Amendment Change 3.

Old text: A total of ~~40~~ children who took at least one dose of study medication are planned to be enrolled in the study. The sample size does not originate from a formal sample size calculation, but is based on a feasibility assessment because of the very low incidence of venous thrombosis in children, and on the pharmacokinetic moderate inter-individual variability of rivaroxaban. Based on past experience in obtaining parental consent in this indication, it is estimated that fewer than 10% of eligible children can be enrolled in this study.

New text: A total of 20 children who took at least one dose of study medication are planned to be enrolled in the study. The sample size does not originate from a formal sample size calculation, but is based on a feasibility assessment because of the very low incidence of venous thrombosis in children, and on the pharmacokinetic moderate inter-individual variability of rivaroxaban. Based on past experience in obtaining parental consent in this indication, it is estimated that fewer than 10% of eligible children can be enrolled in this study.

16.2.2.39 Section 7.9: Adverse events (AE)

This section was modified based on Amendment Change 2.

Old text: Individual listings of adverse events (including ~~treatment group~~, age, weight, height, gender, adverse event as reported, start, duration, severity and relation to study drug) will be provided. The incidence of treatment-emergent adverse events will be summarized by ~~treatment~~ using MedDRA preferred terms grouped by primary system organ class.

New text: Individual listings of adverse events (including age, weight, height, gender, adverse event as reported, start, duration, severity and relation to study drug) will be provided. The incidence of treatment-emergent adverse events will be summarized by age group using MedDRA preferred terms grouped by primary system organ class.

16.2.2.40 Section 7.9.9: AEs of special safety interest

This section was modified based on Amendment Change 6.

Old text: [...]

- A platelet count below ~~100~~ x 10⁹/L.

New text: [...]

- A platelet count below 50 x 10⁹/L.

17. Appendices

17.1 Methods and measurements

Bioanalytics and pharmacokinetics

Rivaroxaban concentrations in plasma will be measured by a validated high-performance liquid chromatography assay with tandem mass spectrometric detection. Quality control and calibration samples will be analyzed concurrently with study samples. The results of quality check samples will be reported together with concentrations in unknown samples in the clinical study report. Concentrations are calculated from the chromatographic raw data in accordance with current Bayer guidelines. Only values above the lower limit of quantification are used to determine pharmacokinetic parameters.

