Check if anticoagulant treatment continued after Visit 4					•	
Complete eCRF	•	•	•	•	•	
Pharmacokinetics and pharmacodynamics ^f						
	Visit 1	Visit 2		Visit 3	Visit 4	Visit 5
Time point (hours)		0.5-1.5 hr post dose	2.5-4 hr post dose	2-8 hr post dose	10-16 hr post dose	
Obtain blood sample for pharmacokinetics ^h		•	•	•	•	
Obtain blood sample for pharmacodynamics ^{ij}			•	•	•	
Administer rivaroxaban at study site ^k		•	•			
Complete Taste-and-Texture Questionnaire ^l			•			

for footnotes please see following page

[figure not shown]

^a The screening visit can be performed up to 60 days prior to Visit 2, but should not be less than 10 days prior to Visit 2. Please contact the adjudication office in case the available period prior to Visit 2 is less than 10 days.
 
^b Results should be available within 10 days prior to Visit 2, if not obtain blood sample at visit 2.
 
^c Done before the study drug intake.
 
^d If suspected outcome occurred, the adjudication package needs to be compiled and sent to the adjudication office.
 
^f The approximate total blood volume taken per child is 10 mL if blood taken via venipuncture, and 22 mL if blood taken via central venous line or peripheral catheter.
 
^g PK/PD sampling only if the child received rivaroxaban for more than 3 days
	
^h Blood volume per PK sample is 1.2 mL; total blood volume for all PK samples is 4.8 mL
 
ⁱ Blood volume per PD sample is 1.8 mL; total blood volume for all PD samples is 5.4 mL
 
^j Always draw the pharmacodynamic sample as the last sample
 
^k For switching from heparin, LMWH/fondaparinux, VKA see section 5.1.1
 
^l Taste and texture questionnaire to be completed in part before and after the study drug intake (only children > 4 years old) ¹⁵
 
eCRF: electronic case report form; Hb: Hemoglobin; INR: International normalized ratio; IxRS: interactive voice/web response system

---	---

¹⁵ Flow chart modified via Amendment 4 (see Section 16.2.2.2)

Blood pressure levels for children

Figure 1–2: Age percentiles for blood pressure in children from birth to 12 months of age

Source: (15)

Table 1–1: Age and Height percentiles for blood pressure in children from 1 to 6 years of age

Boys														
Age	Systolic blood pressure, mmHg							Diastolic blood pressure, mmHg						
	Percentile of height							Percentile of height						
	5th	10th	25th	50th	75th	90th	95th	5th	10 th	25th	50th	75 th	90th	95th

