6.12 PK/PD assessments - amended

Blood samples will be taken for PK and PD measurements.⁴⁴ The number and volume of PK/PD blood samples represents the minimum amount of blood needed for adequate analysis (sparse sampling approach). The following blood samples will be taken:

- 1) PK/PD samples at visit 2,
- 2) PK/PD sample at visit 3, and
- 3) PK/PD sample at visit 4.

⁴² Comparator arm was removed via Amendment 4 (see Section 16.2.2.30)

⁴³ Section modified via Amendment 4 (see Section 16.2.2.31)

⁴⁴ Section modified via Amendment 4 (see Section 16.2.2.32)

The exact time of rivaroxaban dosing and PK/PD blood sampling will be documented in the eCRF. If, for any reason, PK/PD samples are taken outside of the pre-specified time window, the exact time that the sample was taken should be recorded and not the time of the time window.

If rivaroxaban was temporarily stopped at the time of a study visit (e.g. if treatment was temporarily stopped prior to visit 3), sampling of blood for PK/PD analysis according to this visit's schedule should be postponed until rivaroxaban treatment has been restarted and sustained for at least 3 days.

If a blood sample is taken from a central line, 3 mL of blood should be discarded.⁽¹⁶⁾ In children from 6 months to 1 year old, it might not be possible to withdraw blood from central venous line due to the amount of blood required especially at visit 2. In this case, it is advised to withdraw blood from a peripheral catheter. If a blood sample is taken from a peripheral catheter, fluid is to be withdrawn from the line until all is removed and blood is sampled. An anesthetic cream can be applied to minimize pain from drawing of blood from a vein. Central venous lines and peripheral catheters that are used in this study should only be flushed with saline.

The prothrombin time, activated partial thromboplastin time and anti-factor Xa activity (anti-Xa) will be used to assess the pharmacodynamic effects after administration of the study drug.

Detailed information about the handling and labeling of the samples will be provided in the laboratory manual.

The data obtained from the blood samples taken will be pooled and analyzed using population approaches to estimate the PK/PD profile of rivaroxaban. Details for the population PK/PD analysis will be described in a separate evaluation plan.

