6.4 Pharmacokinetics / pharmacodynamics

Individual profiles and summary statistics overall and by weight groups will be provided for PK/PD data. PK/PD modeling, using population approaches will be used to describe the pharmacokinetics of rivaroxaban, including potential influence of relevant co-variables, and relation of anticoagulant parameters of rivaroxaban with plasma concentrations. Details will be given in a separate PK/PD evaluation plan.

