6.5.3 Laboratory measurements

Descriptive statistics will be presented for Hb, platelets, ALT, total and direct bilirubin at visit 4 (Day 30) and for their changes to baseline. The descriptive statistics will be done for all data combined and for each age cohort. Additional lab data at visit 3 (Day 15) and their changes to baseline will be summarized for patients from Canada separately. For the calculation of the mean value an anti-Xa activity value below LLOQ will be substituted by one half of this limit. In tables showing descriptive statistics, where values below LLOQ are included in the calculation of mean values, these means will be marked. All other lab values including aPTT and PT with the qualifier '< i.e less than' will be considered for descriptive statistics with their values without the qualifier. All lab values with the qualifier '> i.e. greater than' will be considered for descriptive statistics with their values without the qualifier.

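### Protocol 17.1 leaves concentrations below the LLOQ out of PK parameter estimation; if any Visit 4 samples fall there, late-phase parameters and estimated trough exposure can be biased upward

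*Protocol*

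**What the plan says.** Protocol 17.1 describes the plasma assay and then sets the rule: "Only values above the lower limit of quantification are used to determine pharmacokinetic parameters". No other rule for plasma concentrations below the LLOQ appears in either document.

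The sampling is sparse. Figure 1-1 and Protocol 6.3 to 6.5 plan two samples on Day 1 (0.5-1.5 h and 2.5-4 h after the dose), one at Visit 3 (2-8 h) and one at Visit 4 (10-16 h). Dosing is every 12 hours (Protocol 5.1.1).

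For the analysis, Protocol 6.12 states: "The data obtained from the blood samples taken will be pooled and analyzed using population approaches". SAP 6.4 adds individual profiles, summary statistics, and a model for the "relation of anticoagulant parameters of rivaroxaban with plasma concentrations". Protocol 6.12 and 7.6 and SAP 6.4 leave the modelling details to a separate PK/PD evaluation plan.

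For anti-Xa, SAP 6.5.3 has a different rule: "For the calculation of the mean value an anti-Xa activity value below LLOQ will be substituted by one half of this limit". It adds that "where values below LLOQ are included in the calculation of mean values, these means will be marked".

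**The concern.** A result below the LLOQ is not a missing value. It says that the concentration was lower than a known number. The rule in 17.1 removes such a result because it is low, so the loss depends on the outcome and runs in one direction.

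The sample most exposed to this is the Visit 4 draw, since nothing else is planned later than 8 h after a dose. The morning dose is held back before Visit 3, but no pre-dose sample is taken there. If some Visit 4 values are below the LLOQ, they will tend to come from children who eliminate the drug faster, and the remaining late data will over-represent the slower ones.

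The PK/PD profile is a secondary objective, and the regimen aims at an exposure like that of adults on 20 mg once daily. An upward bias at the low end would make exposure look better matched than it is. With 10 children per age group, two excluded Visit 4 values are 2/10 = 20% of that group's late PK data.

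**Working it through.** The plan gives no figure to reproduce: it states no LLOQ, expected share below it, trough level or half-life, and its sample size has no formal calculation. The check shows how large the effect would be over assumed ranges.

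**Inputs from the documents**
- PK samples per child, from the footnotes to Figure 1-1: "Blood volume per PK sample is 1.2 mL; total blood volume for all PK samples is 4.8 mL", so 4.8/1.2 = 4, of which one is at 10-16 h.
- PD samples per child, from the same footnotes: 5.4/1.8 = 3, each drawn with a PK sample.
- Children: 20, 10 per age group (Protocol 4.1).
- Between-child variability: called moderate in Protocol 7.8, with no number.

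**Assumed:** Visit 4 concentrations lognormal with CV 30-70%; share f below the LLOQ from 1% to 30%.

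**Step 1. Would the rule come into play?** The chance that none of 20 Visit 4 samples is below the LLOQ is (1 - f)^20: 0.82 at f = 1%, 0.36 at 5% and 0.12 at 10%.

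**Step 2. Trough.** Let σ = √ln(1 + CV²) and let z be the standard normal quantile at f. The geometric mean of the retained values, divided by the true one, is exp[σ·φ(z)/(1 - f)].
- CV 30% gives σ = 0.294; CV 70% gives σ = 0.631.
- f = 10%: φ(z)/(1 - f) = 0.1755/0.9 = 0.195. The ratios are exp(0.294 × 0.195) = 1.059 and exp(0.631 × 0.195) = 1.131.
- f = 20%: 0.280/0.8 = 0.350. The ratios are exp(0.294 × 0.350) = 1.108 and exp(0.631 × 0.350) = 1.247.

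| Share below LLOQ | CV 30% | CV 50% | CV 70% |
|---|---|---|---|
| 1% | +0.8% | +1.3% | +1.7% |
| 5% | +3.2% | +5.3% | +7.1% |
| 10% | +5.9% | +9.6% | +13.1% |
| 20% | +10.8% | +18.0% | +24.7% |
| 30% | +15.7% | +26.4% | +36.8% |

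The same model shows where the LLOQ must lie, as a fraction exp(σz) of the median Visit 4 concentration. For f = 10% (z = -1.282) it is 0.69 at CV 30% and 0.45 at CV 70%. For f = 20% (z = -0.842) it is 0.78 and 0.59.

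**Step 3. Half-life in a population model.** Decline-phase samples were simulated in the protocol windows (2.5-4, 2-8 and 10-16 h). The assumptions were a median half-life of 3 h, a CV of the elimination rate of 30% or 50%, a CV of level of 40%, and a residual SD of 0.25 on the log scale. A mixed model with values below the LLOQ dropped was compared with a censored-likelihood fit to the same data. Each cell is three runs of 250 children, so it indicates size only roughly.

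| Share below LLOQ | Rate CV | Dropped (h) | Censored (h) | Ratio |
|---|---|---|---|---|
| 5% | 30% | 2.96 | 2.92 | 1.01 |
| 10% | 30% | 3.08 | 2.97 | 1.04 |
| 20% | 30% | 3.20 | 2.95 | 1.08 |
| 30% | 30% | 3.37 | 3.09 | 1.09 |
| 5% | 50% | 2.97 | 2.85 | 1.04 |
| 10% | 50% | 3.24 | 3.23 | 1.00 |
| 20% | 50% | 3.08 | 2.86 | 1.08 |
| 30% | 50% | 3.25 | 3.01 | 1.08 |

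The inflation is about 0-4% with 5-10% below the LLOQ and 8-9% with 20-30% below. A naive pooled log-linear fit does worse: with 30% below, half-life goes from 2.86 to 3.80 h (+33%) or from 2.56 to 4.19 h (+64%). That is not the planned analysis.

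**The case against.** The strongest reply is that the effect may not exist. The assay is validated chromatography with tandem mass spectrometry, and Step 2 shows that even 10% below the LLOQ would need a limit at about 45-69% of the median Visit 4 concentration. Nothing in the documents points to so insensitive an assay. A population model also keeps the child's other three samples, which is why Step 3 gives small numbers. The modelling is deferred to an evaluation plan that is not among the documents and may already handle censored values. Half-life is not a named parameter, and the primary objective, bleeding, is untouched.

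Most of this stands as a limit on size. The deferral does not remove the point: 17.1 either governs the evaluation plan or contradicts it, and in both cases the sentence needs attention.

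A reader might also draw stronger conclusions, which the documents do not support:
- **The two LLOQ rules collide in one model.** The half-LLOQ rule is confined to calculating anti-Xa means, and those means are marked. Nothing carries it into the concentration-effect model.
- **The low end of the concentration-effect relation is lost.** Only pairs whose concentration is below the LLOQ would drop out; low but quantifiable values stay.
- **Children with low exposure disappear from view.** 17.1 restricts parameter determination, not reporting. It has sample concentrations reported in the study report, and SAP 6.4 plans individual profiles.
- **The early Day 1 sample is equally at risk because the suspension releases slowly.** The rationale for Amendment 1 (Protocol 16.1.1.2) does report slow release, but it also says that pre-dilution helps restore a tablet-like profile.

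**Conclusion.** The point holds as a modest, conditional one on a secondary objective. As written, 17.1 discards left-censored information in the only late sampling window. If any Visit 4 values are below the LLOQ, the direction of the resulting bias is upward. It would be wrong to infer that bias is certain: it is zero if no sample is below the LLOQ.

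If 10% are below, the geometric mean of the retained troughs is about 6-13% too high; at 20% it is 11-25%. These figures assume lognormal concentrations with CV 30-70%, and they describe a trough summary only if that summary also leaves out the values below the LLOQ. Section 17.1 does not cover descriptive summaries, and SAP 6.4 gives no rule for them. The half-life inflation of about 0-4% (5-10% below) and 8-9% (20-30% below) rests on the assumed 3 h half-life and a small simulation.

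**What to change.** Replace the sentence in Protocol 17.1 and put the same rule in the PK/PD evaluation plan, so that the two agree. Suggested wording:

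*Post-dose concentrations below the LLOQ are retained as left-censored observations in the population model (likelihood-based M3 method). An analysis that excludes them is reported as a sensitivity check. The number of concentrations below the LLOQ is reported by visit and age group.*

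Stating the LLOQ next to those counts would let a reader judge at once whether the issue arises. Substituting half the LLOQ for anti-Xa can stay, for the descriptive table only.

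The cost is a few sentences and a standard modelling option, with no new samples. The downside is slightly longer run time and possibly some convergence work. If no concentration is below the LLOQ, the two analyses coincide.
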